5.3 SAMPLE STORAGE, TRACKING AND DISPOSITION

Samples will be ordered in CRIS and tracked through a Clinical Trial Data Management system. Should a CRIS screen not be available, the CRIS downtime procedures will be followed. Samples will not be sent outside the National Institutes for Health (NIH) without appropriate approvals and/or agreements, if required.

5.3.1.1 Sample Data Collection

All samples sent to the Blood Processing Core (BPC) will be barcoded, with data entered and stored in Labmatrix utilized by the BPC. This is a secure program, with access to Labmatrix limited to defined [name] lab personnel, who are issued individual user accounts. Installation of Labmatrix is limited to computers specified by [name]. These computers all have a password restricted login screen.

Labmatrix creates a unique barcode ID for every sample and sample box, which cannot be traced back to participants without Labmatrix access. The data recorded for each sample includes the participant ID, name, trial name/protocol number, time drawn, cycle time point, dose, material type, as well as box and freezer location. Participant demographics associated with the clinical center patient number are provided in the system. For each sample, there are notes associated with the processing method (delay in sample processing, storage conditions on the ward, etc.).

5.3.1.2 Sample Storage and Destruction

Barcoded samples are stored in barcoded boxes in a locked freezer at either -20°C or -80°C according to stability requirements. These freezers are located onsite in the BPC and offsite at NCI Frederick Central Repository Services in Frederick, MD. Visitors to the laboratory are required to be accompanied by laboratory staff at all times.

Access to stored clinical samples is restricted. Samples will be stored until requested by a researcher named on the protocol. All requests are monitored and tracked in Labmatrix. All researchers are required to sign a form stating that the samples are only to be used for research purposes associated with this trial (as per the IRB approved protocol) and that any unused samples must be returned to the BPC. It is the responsibility of the NCI Principal Investigator to ensure that the samples requested are being used in a manner consistent with IRB approval.

Following completion of this study, samples will remain in storage as detailed above. Access to these samples will only be granted following IRB approval of an additional protocol, granting the rights to use the material.

If, at any time, a participant withdraws from the study and does not wish for their existing samples to be utilized, the individual must provide a written request. Following receipt of this request, the samples will be destroyed (or returned to the participant, if so requested). The PI will record any loss or unanticipated destruction of samples as a deviation. Reporting will be per the requirements of Section [7.2](#).

Sample barcodes are linked to participant demographics and limited clinical information. This information will only be provided to investigators listed on this protocol, via registered use of the Labmatrix. It is critical that the sample remains linked to participant information such as race, age, dates of diagnosis and death, and histological information about the tumor, in order to correlate genotype with these variables.

5.3.2 Laboratory of Pathology

Tissues designated for clinical diagnostics are transported to the Laboratory of Pathology (LP) where they are examined grossly, and relevant portions are fixed, embedded in paraffin and sectioned and stained for diagnostic interpretation. Unutilized excess tissues are stored for up to three months, in accordance with College of American Pathologists/Joint Commission on Accreditation of Healthcare Organizations (CAP/JCAHO) guidelines, and then discarded.

Following completion of the diagnostic workup, the slides and tissue blocks are either returned to the originating pathology department if requested or stored indefinitely in the LP's clinical archives. All specimens are catalogued and retrieved utilizing the clinical laboratory information systems, in accordance with CAP/JCAHO regulations. The use of any stored specimens for research purposes is only allowed when the appropriate IRB approval has been obtained. In some cases, this approval has been obtained via the original protocol on which the participant was enrolled.

5.3.3 Center for Cancer Research Sequencing Facility (CCR-SF)

The Center for Cancer Research Sequencing Facility (CCR-SF), frequently referred to as the NCI Frederick Sequencing Facility, is a CCR-dedicated sequencing core facility at the Frederick National Laboratory for Cancer Research (operated by Leidos Biomedical Research, Inc. and sponsored by NCI). The Sequencing Facility processes genomics samples such as DNA or RNA from CCR investigators for genomics analysis including mutation analysis such as whole genome sequencing, transcript profiling and discovery, DNA/RNA protein interaction, exome sequencing or targeted exome sequencing and gene expression analysis.

5.3.3.1 Sequencing Facility Established Procedures of Sample Receiving and Storage

- Samples are received with a service request through the secure online request system (NAS).
- Samples must be coded by the sender to remove any PII. The Sequencing Facility will not receive any samples with PII and does not store such information within their electronic database system (LIMS).
- Samples are inventoried and stored in freezers or refrigerators which are monitored through the alarm system.
- The facility's laboratory is located within a controlled access building.
- Samples are tracked in LIMS in addition to hard copy sample logs.
- Sequencing Facility personnel receive annual updated NIH/CIT training and maintain standards of computer security.
- At the end of the project, leftover samples (if any) will be transferred back to the requestor. The Sequencing Facility does not provide long term storage.

5.3.4 Laboratory of [name]

Samples collected for the purpose of research under this protocol may undergo DNA/RNA extraction in [name] lab after Blood Processing Core (BPC) barcoding, initial processing, and storage. Samples are stored in freezers at -80°C or -20°C according to stability requirements. Samples will be sent on for protocol research analysis as directed by the Principal Investigator.

5.3.5 Protocol Completion/Sample Destruction

All specimens obtained in the protocol are used as defined in the protocol. Any specimens that are remaining at the completion of the protocol will be stored in the conditions described in sections above. The study will remain open so long as sample or data analysis continues. Samples from consenting subjects will be stored until they are no longer of scientific value or if a subject withdraws consent for their continued use, at which time they will be destroyed.

If the patient withdraws consent the participant's data will be excluded from future distributions, but data that have already been distributed for approved research use will not be able to be retrieved.

The PI will record any loss or unanticipated destruction of samples as a deviation. Reports will be made per the requirements of Section [7.2.1](#).

5.3.6 Machine Learning for Early Gastric Cancer Detection

Application of artificial intelligence to radiographic and histopathologic tests is being explored to improve the sensitivity and specificity of cancer diagnosis. Because the use of CEM in our previous Phase II study showed low sensitivity for occult cancer detection, we believe that application of machine learning (i.e., computer models) based on the input provided by CEM imaging, and endoscopic high-resolution video imaging as applicable, will improve our ability to accurately and reliably detect cancer. By incorporating the corresponding histopathology images/results obtained after gastric biopsy, we will essentially teach the computer how to reliably detect occult gastric cancer through an iterative process.

This machine learning for early cancer detection is ONLY being applied post-hoc as a research tool to improve endoscopic diagnosis for protocol endpoints– it will not be used in any way to diagnose or treat patients enrolled on this study.

6 DATA COLLECTION AND EVALUATION

6.1 DATA COLLECTION

The PI will be responsible for overseeing entry of data into a data capture system provided by the NCI CCR and ensuring data accuracy, consistency and timeliness. The principal investigator, associate investigators/research nurses and/or a contracted data manager will assist with the data management efforts. Primary and final analyzed data will have identifiers so that research data can be attributed to an individual human subject participant.

All adverse events, including clinically significant abnormal findings on laboratory evaluations, regardless of severity, will be followed until return to baseline or stabilization of event.

Document AEs from the start of endoscopy through 14 days following study interventions.

An abnormal laboratory value will be recorded in the database as an AE **only** if the laboratory abnormality is characterized by any of the following:

- Results in discontinuation from the study
- Is associated with clinical signs or symptoms
- Requires treatment or any other therapeutic intervention
- Is associated with death or another serious adverse event, including hospitalization.
- Is judged by the Investigator to be of significant clinical impact
- If any abnormal laboratory result is considered clinically significant, the investigator will provide details about the action taken with respect to the test drug and about the patient's outcome.

Adverse Events related to study interventions will **only** be recorded if they are serious (all Grades) or unexpected (Grades 3 and above).

We will collect information from participants regarding consuming nutritional or dietary supplementation, antimicrobial medications, pro- or prebiotics, and/or laxative agents; this information may be recorded in the participant's medical record (in addition to the data capture system provided by the NCI CCR) as applicable.

End of study procedures: Data will be stored according to HHS, FDA regulations, and NIH Intramural Records Retention Schedule as applicable.

Loss or destruction of data: Should we become aware that a major breach in our plan to protect subject confidentiality and trial data has occurred, this will be reported expeditiously per requirements in Section [7.2.1](#).

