3.1.1 Bethesda Protocol, Arm 1 (Investigational Arm)

Participants will undergo white light endoscopy. The mucosa of the stomach may be thoroughly washed before examination with a combination of mucolytics (N-acetylcysteine) and anti-foaming agents (simethicone) mixed with sterile water, as medically indicated. Inspection will include repeated inflation and deflation to check distensibility and any abnormal appearing areas will additionally be biopsied. Eighty-eight non-targeted biopsies from 22 areas of the stomach, four mucosal biopsies from each, will be obtained using standard cold endoscopic forceps. This technique is estimated to take approximately 45 minutes or less.

- Antrum, antegrade view – anterior (1), lesser curve (2), posterior (3), greater curve (4)
- lower body, antegrade view – anterior (5), lesser curve (6), posterior (7), greater curve (8)

- middle-upper body, antegrade view – anterior (9), lesser curve (10), posterior (11), greater curve (12)
- fundus-cardia, retroflex view – anterior (13), lesser curve (14), posterior (15), greater curve (16)
- middle-upper body, retroflex view – anterior (17), lesser curve (18), posterior (19)
- incisura, retroflex view – anterior (20), lesser curve (21), posterior (22)

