3.1.2 Cambridge Method Upper Endoscopy, Arm 2 (Control Arm)

Participants will undergo white light endoscopy. The mucosa of the stomach may be thoroughly washed before examination with a combination of mucolytics (N-acetylcysteine) and anti-foaming agents (simethicone) mixed with sterile water, as medically indicated. Inspection will include repeated inflation and deflation to check distensibility and any abnormal appearing areas will additionally be biopsied. A minimum of 30 non-targeted biopsies will be obtained from 6 anatomic zones of the stomach:

- pre-pyloric area,
- antrum,
- transitional zone,
- body,
- fundus, and
- cardia.

Five mucosal biopsies will be taken from each zone. Biopsies will be taken using standard, cold endoscopic forceps. This technique is estimated to take approximately 30 minutes or less.

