3.3 FOLLOW-UP

Patients will return to the NIH Clinical Center approximately two weeks after the EGD to discuss pathology results and any adverse events that they might have experienced. Alternatively, we will discuss pathology results and adverse events (AEs) on the phone.

Gastrectomy is not part of this protocol, but if patient elects to undergo gastrectomy on another protocol, we may perform additional correlative studies before, during and after gastrectomy, including pathology assessment of stomach tissue.

Participants declining total gastrectomy (TG) may be invited to collect stool samples after study intervention as indicated in Section [5.1](#).

Participants who elect for TG may be invited to collect stool, blood and oropharyngeal swab/saliva samples pre-gastrectomy and post-gastrectomy as indicated in Section [5.1](#).

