9.4 RISK/BENEFIT ASSESSMENT FOR ALL PARTICIPANTS

9.4.1 Known Potential Risks

9.4.1.1 Risks of Upper Endoscopy

The risks of upper endoscopy include, but are not limited to, temporary throat soreness, gastrointestinal bleeding, and rarely gastrointestinal perforation.

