9.4.1.4 Risk of Biopsies

All care will be taken to minimize risks that may be incurred by tumor sampling. Biopsies will be taken during endoscopy. All procedure-related risks (such as bleeding, infection and visceral injury) will be explained fully during informed consent.

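### Section 6.1 leaves non-serious, expected procedure-related events unrecorded, so the trial cannot describe the non-serious safety cost of 88 versus at least 30 biopsies

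*Combined protocol and SAP*

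**What the plan says.** Four parts of the protocol bear on this.

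- **Recording rule (6.1 Data Collection).** Events related to study interventions will only "be recorded if they are serious (all Grades) or unexpected (Grades 3 and above"). Separately, the same section says "Document AEs from the start of endoscopy through 14 days following study interventions", with no limit by grade, seriousness or relatedness.
- **Biopsy burden (3.1.1 and 3.1.2).** Arm 1: "Eighty-eight non-targeted biopsies from 22 areas of the stomach, four mucosal biopsies from each". Arm 2: "A minimum of 30 non-targeted biopsies will be obtained from 6 anatomic zones of the stomach". Abnormal-looking areas are biopsied in addition in both arms.
- **Known risks (9.4.1).** For upper endoscopy, 9.4.1.1 lists "temporary throat soreness, gastrointestinal bleeding, and rarely gastrointestinal perforation". For biopsy, 9.4.1.4 says "All procedure-related risks (such as bleeding, infection and visceral injury) will be explained fully during informed consent".
- **Contact after the procedure (3.3 and 3.5).** About two weeks after the endoscopy there is a visit or call "to discuss pathology results and any adverse events that they might have experienced", and 3.5 asks for a safety visit at about 14 days.

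Section 6.3 specifies CTCAE version 5.0. Section 9.4.3 states that potential benefit outweighs risk. The objectives (1.1) and Section 8 contain no safety endpoint and no comparison of adverse events between arms.

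**The concern.** The trial tests a method that takes roughly three times as many biopsies as the control method. Biopsy-related harm is where the two arms would most plausibly differ on safety. The filter in 6.1 applies only to related events, so it removes the non-serious part of exactly that harm. A mild unrelated event is untouched by the filter, while a mild biopsy bleed is dropped.

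At stake is the account of what the extra biopsies cost the patient. The trial could report a gain in detection with no measured non-serious harm to set beside it, although 9.4.3 asserts a favourable balance. Patients are already asked about adverse events at the two-week contact, so the information would be elicited and then not kept as trial data.

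**Working it through.** **Step 1: what the recording rule keeps.** Applying the 6.1 sentence to intervention-related events:

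| Related event | Expected | Unexpected |
|---|---|---|
| Serious, any grade | recorded | recorded |
| Non-serious, Grade 3 and above | not recorded | recorded |
| Non-serious, Grade 1-2 | not recorded | not recorded |

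Section 7.1 sends definitions to an outside policy, and the protocol text does not define expected. If the risks listed in 9.4.1 count as expected, bleeding falls in the left column and is lost at every grade unless serious. If bleeding were unexpected, only the middle row changes. Non-serious Grade 1-2 bleeding is lost either way.

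**Step 2: the text in 6.1 side by side.** The instruction to document events to day 14 carries no restriction. The later sentence restricts related events. The section does not say whether the first sets only a time window or also sets the content. A third rule, on which abnormal laboratory values are recorded as adverse events, is not ranked against the related-event rule either. Staff could apply 6.1 in more than one way.

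**Step 3: biopsy burden.** Arm 1: 22 × 4 = 88, and the sites listed in 3.1.1 sum to 4 + 4 + 4 + 4 + 3 + 3 = 22. Arm 2: 6 × 5 = 30, stated as a minimum. Ratio: 88/30 = 2.93. If the two research biopsies in 5.1.1.2 are taken in both arms, it is 90/32 = 2.8. Targeted biopsies would change it further.

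**Step 4: check of the method and the per-arm number.** The documents give no bleeding rate and no safety power, so there is no safety figure to reproduce. Power below is the sum, over all pairs of event counts, of their binomial probabilities where the two-sided Fisher p-value is at most 0.05. Applied to the plan's crude detection rates in 8.2 (15% v 30%), this gives 90.6% at 175 per arm and 81.0% at 135 per arm. Both match the plan.

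**Step 5: illustration under assumed rates.** The assumptions are 175 per arm (the planned maximum) and bleeding risk proportional to biopsy number (ratio 2.93). All rates are assumed.

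| What is compared | Cambridge v Bethesda | Expected events | Power |
|---|---|---|---|
| Serious only | 0.5% v 1.5% | 0.9 v 2.6 | 2% |
| Serious only | 1% v 2.9% | 1.8 v 5.1 | 12.5% |
| All grades | 2% v 5.9% | 3.5 v 10.3 | 35% |
| All grades | 5% v 14.7% | 8.8 v 25.7 | 83.5% |
| All grades | 10% v 29.3% | 17.5 v 51.3 | over 99% |

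Expected events are 175 × rate, for example 175 × 0.05 = 8.75. If the rates differed less than in proportion to biopsy number, say 2% v 5% (3.5 v 8.75 events), power would be about 22% even with every event recorded.

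**The case against.** The strongest reply is that no planned analysis is broken. This is a detection trial with no safety objective, and asking for a safety table is a design preference. That stands: the primary and secondary results are untouched. Patient-level oversight also exists. The research team discusses each patient weekly, and under 7.4.1 the principal investigator reviews adverse events, with nothing limiting that review to database entries. This protects individual patients, but it does not produce a summary by arm.

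Three stronger readings are tempting and are not supported.

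- **That bleeding cannot be compared between arms at all.** Serious bleeding of any grade is recorded and can be tabulated. Only the non-serious part is lost.
- **That the rule contradicts the sentence on events of any severity.** That sentence says events, "regardless of severity, will be followed until return to baseline or stabilization of event". It is a duty to follow events, and an event can be followed clinically without being entered as trial data. The real tension is with the unrestricted instruction to document events. Even that could be read as setting only the time window, so it calls for reconciliation and is not a proven contradiction.
- **That the reported safety table would be falsely clean.** The plan contains no such table. One correctly labelled as serious or unexpected Grade 3 and above would be incomplete, not false.

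It is also fair to say that the bleeding rates are assumed, and that at low rates full recording would describe the harm without establishing a difference.

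**Conclusion.** The point holds in limited form. Followed as written, 6.1 drops non-serious intervention-related events unless they are unexpected and Grade 3 or above. The arms differ by 88 v at least 30 non-targeted biopsies, so the trial cannot describe the non-serious safety cost of the larger set. Serious bleeding remains comparable, but probably with little power: about 2% to 12.5% under the assumed control rates of 0.5% to 1%.

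The loss of Grade 3 and above non-serious bleeding depends on treating the 9.4.1 risks as expected. The loss of Grade 1-2 non-serious bleeding does not. The power figures rest on assumed rates, on risk proportional to biopsy number and on 175 per arm, and they serve only to show scale. This is a cheap and worthwhile improvement to data capture. It does not threaten the validity of the primary comparison.

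**What to change.** 1. Reconcile the recording rule in 6.1 with the instruction to document events to day 14, and state in the text what counts as expected.
2. Record every endoscopy- or biopsy-related event from the start of endoscopy to day 14, with its CTCAE grade. At minimum this covers bleeding, perforation and infection of any grade. Use the two-week contact that already takes place.
3. Keep the serious/unexpected filter for expedited reporting only.
4. Add to Section 8 a descriptive table by arm, with 95% confidence intervals, for all patients who undergo endoscopy. No hypothesis test is needed.
5. If the change comes during accrual, report patients enrolled before and after it separately, or recover earlier events from the medical record where documented, so that two capture rules are not silently mixed.

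The cost is a few form fields, one table, a small extra data-entry load and, for a change during accrual, a mixed capture period to explain. The change affects data capture only, not clinical management.

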6.2 DATA SHARING PLANS

6.2.1 Human Data Sharing Plan

The PI will share coded linked human data generated in this research for future research:

- in a NIH-funded or approved public repository clinicaltrials.gov, GenBank

- in BTRIS
- in publication and/or public presentations
- with approved outside collaborators under appropriate agreements
- at the time of publication or shortly thereafter.

6.2.2 Genomic Data Sharing Plan

Bacterial gene sequences will be deposited in GenBank.

6.3 TOXICITY CRITERIA

The following adverse event management guidelines are intended to ensure the safety of each patient while on the study. The descriptions and grading scales found in the revised NCI Common Terminology Criteria for Adverse Events (CTCAE) version 5.0 will be utilized for AE reporting. All appropriate treatment areas should have access to a copy of the CTCAE version 5.0. A copy of the CTCAE version 5.0 can be downloaded from the CTEP web site (http://ctep.cancer.gov/protocolDevelopment/electronic_applications/ctc.htm#ctc_50).

